### *Hot Water Immersion Therapy*

Previous reports have demonstrated that benefits from heat therapy require 5-14 days to become apparent. Thus, participants in the present study will undergo 8-10 shoulder-high hot water immersions of 40.5°C for 45 minutes/session during a 14-16-day period. Either 1) a rectal probe with sterile disposable sheaths or 2) a sterile rectal thermistor probe will be used to monitor the subject's temperature ( $T_{re}$ ). These probes are inserted approximately 2.54 cm past the anal sphincter. The subject will be removed from the hot tub if  $T_{re}$  is 38.5°C or higher. Participants will be asked to sit on a bench of the hot tub with until  $T_{re}$  is < 38.0°C at which time they may return to the hot tub. Participants are able to drink water *ad libitum* while in the hot tub.  $T_{re}$  will be monitored for 10 additional minutes following emersion from the hot tub or until  $T_{re}$  < 38.0°C.

Hot tub located in the CRC at KUMC.

Subjects will have dry weights measured prior to and after hot water therapy. If body weight loss following therapy is > 1%, the participant will be asked to drink additional fluids to make up the difference. Heart rate will be monitored continuously during heat therapy. If heart rate is altered > 50% from baseline, the participant will

be assessed for neurologic and hemodynamic changes. If there are changes concerning these assessments, the subject will be removed from the hot tub, temperature monitored, and a medical provider notified. Blood pressure will be obtained prior to and after hot water therapy. Participants with pre-therapy systolic blood pressure < 75mmHg or > 180mmHg and/or diastolic blood pressure < 40mmHg or > 90mmHg, will not be allowed to participate in hot water therapy. If post-hot tub blood pressure varies by > 20% lower or > 30% higher than baseline values, the subject will be monitored until return to < 20% deviation from baseline. If blood pressure values do not return to baseline after 10 minutes, discussion with a medical provider will take place prior to discharge from CTSU. If at any time, should a participant become hemodynamically or cognitively impaired during any portion of the study activities, 911 will be called for evaluation and possible transport to the emergency department at TUKH.

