### Study Aim:

#### *Translation of Endothelial Modifications using Heat Therapy into Cardiovascular Fitness Improvement*

In this study, we will assess if the reported improvements in endothelial function translate into improved cardiovascular function. Since heat therapy has been shown to illicit several molecular markers of benefit for endothelial function including enhancement of FMD and other markers of arterial distensibility, there is a potential direct benefit for cardiovascular health and fitness. As of today, these benefits remain theoretical.

Improvements in cardiovascular function are measured by increased exercise tolerance with various strategies of fitness testing. Historically, the gold standard of fitness testing relies on measurements of maximal oxygen consumption ( $VO_{2max}$ ). There are numerous methods to obtaining  $VO_{2max}$ , however some methods are invasive, require significant equipment and/or require intense exercise by the participant. The methods chosen for this study are validated, utilize two different mechanisms of  $VO_{2max}$  measurements in order to enhance reliability, are noninvasive and require minimal exercise in which the participant can rest when needed to ensure safety.

Oxygen consumption testing ( $VO_2$ ) will be measured with a treadmill exercise respirometry study. This test measures  $VO_2$  indirectly by measuring energy expenditure. This method is known as indirect calorimetry and is the gold standard for measuring energy expenditure. Study participants will complete the treadmill exercise respirometry on the day of their first hot tub immersion, prior to the hot tub session. This exercise will also be performed on within 24 to 48 hours of the final hot tub experience.

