#### **Risks:**

##### *Whole-Body Heat Therapy:*

There are some risks associated with heat exposure, including: fatigue, light-headedness, muscle cramps, dehydration, and neurological detriments (i.e. heat stroke). However, these symptoms do not typically occur until core temperature rises above 40°C. Core temperature (rectal thermistor) will be continuously monitored and recorded. Subjects will be removed from the hot bath immediately if either core temperature reaches 39.5°C or the subjects experience any symptoms of heat-related illness. All symptoms subside upon lowering core temperature. Ice packs will be on hand if rapid cooling is necessary (see Rapid Cooling SOP). Heart rate will also be continuously monitored and recorded throughout heating. If HR increases > 60 beats/min above resting or increases > 20 beat/min with a 5 min time period, subjects will be moved to a seated position if they were previously fully submerged, or removed from the hot tub if they were already sitting up. Additionally, heat exposure may have detrimental effect on a developing fetus in females. Thus, subjects who are pregnant or trying to conceive will be excluded from the study. This will be confirmed with a pregnancy test.

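### Two heart-rate rules for the same immersion differ in trigger and in action, with no stated link or precedence between them

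*Protocol*

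**What the plan says.** Two sections of the Protocol govern heart rate during immersion.

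**Hot Water Immersion Therapy.** Monitoring is continuous: "Heart rate will be monitored continuously during heat therapy". The trigger is "If heart rate is altered > 50% from baseline, the participant will" "be assessed for neurologic and hemodynamic changes". The next step is conditional: "If there are changes concerning these assessments, the subject will be removed from the hot tub, temperature monitored, and a medical provider notified".

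**Risks, Whole-Body Heat Therapy.** This section also has heart rate monitored continuously throughout heating. The trigger is "If HR increases > 60 beats/min above resting or increases > 20 beat/min with a 5 min time period". The action is that subjects are "moved to a seated position if they were previously fully submerged, or removed from the hot tub if they were already sitting up".

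Neither section mentions the other's heart-rate rule. *Baseline* and *resting* are not defined in either place, and no time of recording is given for them.

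**The concern.** Both rules apply to the same signal over the same period, but they differ in kind. One is a relative change in either direction. The other is an absolute rise or a rate of rise, upward only. One starts with an assessment; the other goes directly to a move or removal. A reader of either section alone would take it to be the complete heart-rate rule.

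Heart rate and core temperature are the two measures that the Protocol has staff follow continuously in the tub, in participants aged 50 or older. If staff work from one section, an action that the other requires can be missed. There may also be a consequence for the study treatment, planned as 45-minute shoulder-high sessions: a participant moved or removed under one rule but not the other receives a different depth or duration of immersion.

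**Working it through.** The Protocol states no heart-rate figure that can be reproduced, so the check compares the two rules directly.

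**Inputs.** The limits come from the two sections quoted above. The Protocol gives no resting rate, so the reference R is an assumption, shown over a range. *Baseline* and *resting* are taken as the same value R, which is the reading kindest to the plan.

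**Formulas**, with HR the current rate:
- Hot Water Immersion Therapy triggers when |HR − R| / R > 0.5, that is, HR > 1.5R or HR < 0.5R.
- Whole-Body Heat Therapy triggers when HR − R > 60, or when the rise over 5 minutes exceeds 20.

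**Upper limits (beats/min)**

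| Assumed R | 50% limit, 1.5R | +60 limit, R + 60 | Gap | +60 as % of R |
|---|---|---|---|---|
| 60 | 90 | 120 | 30 | 100% |
| 70 | 105 | 130 | 25 | 85.7% |
| 80 | 120 | 140 | 20 | 75% |
| 100 | 150 | 160 | 10 | 60% |
| 120 | 180 | 180 | 0 | 50% |

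The limits coincide where 0.5R = 60, that is, only at R = 120. Below that, the 50% limit is always reached first.

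**The 5-minute criterion.** A rise just over 20 from the reference is 20/60 = 33.3%, 20/70 = 28.6% or 20/80 = 25%. All are below 50%, and this holds for any R above 20/0.5 = 40. So a fast rise can require a move before the assessment limit is reached.

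**Four tracings at R = 70**

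| Tracing | Hot Water Immersion Therapy | Whole-Body Heat Therapy |
|---|---|---|
| 70 to 91 within 5 min (+21; 21/70 = 30%) | not triggered | move to seated, or removal |
| 70 to 106 evenly over 20 min (+36; 36/70 = 51%; 9 per 5 min) | assessment | not triggered |
| 70 to 131 (+61; 61/70 = 87%) | assessment; removal if concerning | move to seated, or removal |
| fall to 34 (−36; 36/70 = 51%) | assessment | not triggered |

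In the first, second and fourth tracings only one section calls for action. In the third both do, but they attach different conditions to leaving the water: in one, the result of an assessment; in the other, whether the participant was already sitting up.

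**The case against.** The strongest reply is that the rules are complementary. Neither excludes the other, and a section whose trigger is not met does not forbid what the other requires. At any reference below 120 the 50% limit comes before +60, so together they could work as a ladder: assess first, then move. Staff who applied the whole Protocol would move the participant in the first tracing and assess in the second and fourth.

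That reading is possible, but the Protocol states it nowhere, and it does not fit cleanly. The 5-minute criterion can require a move before the assessment limit is reached. Above +60, a conditional removal stands beside an unconditional move or removal. The same two sections also give different core temperatures for removal (38.5°C and 39.5°C), which suggests text that was not aligned rather than a planned ladder.

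Other safeguards apply whichever rule is used: removal for symptoms of heat-related illness, the emergency call for hemodynamic or cognitive impairment, termination at CTCAE grade 3 or above, and a safety monitor on the unit. They do not settle the ambiguity, but they lower its weight.

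Four stronger readings are tempting and should not be adopted:
- *That the two reference rates differ.* The words differ, but both are undefined and may mean the same value.
- *That the immersion section permits a participant above +60 to stay in the water.* It gives no such permission; it says only when removal follows an assessment.
- *That the first session's reference is a post-exercise rate.* The Study Aim section does say "Study participants will complete the treadmill exercise respirometry on the day of their first hot tub immersion, prior to the hot tub session". But nothing says that the heart-rate reference is read after the treadmill test or before recovery from it.
- *That the heat dose is changed by a known amount.* The first action for a submerged participant is a move to seated, which reduces depth but not necessarily time, and the document offers nothing from which total exposure could be worked out.

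**Conclusion.** The point holds as an internal inconsistency. Two heart-rate rules cover the same immersion, with different triggers and different actions, no cross-reference, no stated tiers or precedence, and undefined reference terms. Over assumed references of 60 to 80 the two upper limits lie 20 to 30 beats/min apart, and realistic tracings can be found that trigger either rule without the other. The table values depend on the assumed reference; the difference in triggers and actions does not.

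The practical risk is that staff working from one section omit an action required by the other. An effect on depth or time of immersion is possible but cannot be quantified. Given the other safeguards, and because the rules can be applied together, this is something that should be fixed rather than a critical fault.

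**What to change.** Reconcile the heart-rate text of Hot Water Immersion Therapy and of Risks, Whole-Body Heat Therapy into one rule set, placed in one section and cross-referenced from the other. It should state:
- whether the criteria are tiers or alternatives;
- which action follows each criterion;
- one defined reference value, and when it is recorded in relation to each session.

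The limits and actions are for the sponsor's clinicians to choose; this review takes no view on which are right.

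The cost is a short protocol amendment and matching changes to whatever form staff use during sessions. No extra measurement is needed, because heart rate is already monitored and recorded continuously.

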### *Study Cohort and Safety*

Twenty adults, age 50 or older, will be included in the study. Demographic data required for pertinent calculations will be obtained from each participant including height, weight, age and gender. Exclusion criteria includes current major cardiovascular disease known to the patient including recent myocardial infarction, stroke, angina pectoris, high grade coronary vasculopathy or atherosclerosis, severe valvular disease, current cardiac dysrhythmia that requires treatment (i.e. atrial fibrillation, atrial flutter, frequent ventricular premature beats and/or implantation of permanent pacemaker/defibrillator). Patients with a history of coronary artery bypass grafting, valvular surgeries and coronary interventions will be assessed as to current exercise tolerance and symptomology. Other exclusion criteria include current treatment with steroids or immunosuppressive agents, current malignancy, serious liver disease, end-stage renal disease or judgement by a medical provider that water or heat therapy poses an undue burden or risk upon the individual. All females of child bearing age will consent to pregnancy testing and will be excluded if pregnant. Should a participant become hemodynamically or cognitively impaired during any portion of the study activities, 911 will be called for evaluation and possible transport to the emergency department at TUKH. Volunteers can choose to recuse themselves from any or all of the study activities at any time.

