#### *Cardiovascular performance: Oxygen consumption measurements*

Study participants will complete the treadmill exercise respirometry at their first study visit. This exercise will also be performed on within 24 to 48 hours of the final hot tub experience. This waiting period will obviate the transient enhancements of cardiac output and systemic vascular resistance due to water immersion that may alter  $VO_{2max}$  assessments. These effects are normalized shortly after removal from the water and heat sources, thus should be normalized and not have impact on  $VO_{2max}$  by this time. This waiting period also allows for muscle rest prior to the exercise step test. Importantly, waiting until the next day to perform the laboratory and exercise testing also ensures that the changes seen are not acute benefits of heat therapy, but are chronic.

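### The post-immersion blood-pressure rule is relative to baseline throughout and has no absolute limit, so a markedly abnormal pressure at discharge need not prompt a recheck or a provider discussion

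*Protocol*

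**What the plan says.** The rules are in the Protocol, Methods, under Hot Water Immersion Therapy.

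- **Readings taken:** "Blood pressure will be obtained prior to and after hot water therapy".
- **Before immersion, absolute limits.** A participant with "pre-therapy systolic blood pressure < 75mmHg or > 180mmHg and/or diastolic blood pressure < 40mmHg or > 90mmHg" is kept out of the water.
- **After immersion, relative trigger.** "If post-hot tub blood pressure varies by > 20% lower or > 30% higher than baseline values, the subject will be monitored".
- **Release, also relative.** Monitoring continues "until return to < 20% deviation from baseline".
- **Provider discussion, also relative.** "If blood pressure values do not return to baseline after 10 minutes, discussion with a medical provider will take place prior to discharge".

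The same section, like Study Cohort and Safety, has an emergency call for overt haemodynamic or cognitive impairment, with no pressure value attached. The Study Aim section says that ClearSight haemodynamic data, which include blood pressure, are recorded after sessions as well as before and during them. It attaches no action to any value.

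On the population, Study Cohort and Safety says "Twenty adults, age 50 or older, will be included in the study". Hypertension is not among its listed exclusions.

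**The concern.** A percentage rule lets the tolerated pressure rise or fall with the starting pressure. Someone who starts high can finish much higher, and someone who starts low can finish lower still, without crossing the trigger. Release has the same weakness because it too is measured from the starting value.

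The rule is also uneven on the high side. A participant flagged at +31% must stay until below +20%, while one who reads +25% at the first check is never flagged. The band from +20% to +30% therefore counts as not yet recovered for one participant and as needing nothing for another.

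What is at stake is participant safety at discharge. Adults aged 50 or older leave after up to 45 minutes in water at 40.5°C, and staff have no number in mmHg that tells them to recheck or to call a provider.

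**Working it through.** **Inputs** (all from Hot Water Immersion Therapy): entry limits 75-180 mmHg systolic and 40-90 mmHg diastolic; trigger at more than 20% below or more than 30% above baseline; release at less than 20% deviation.

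**Assumption.** The protocol does not define baseline. I take it as that session's pre-therapy reading. The figures are the same if it means the T1 reading and that reading lies within the entry limits. Readings are whole numbers. The entry limits serve only as a yardstick for what the relative rule lets through.

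**Step 1. Extremes that do not trigger** (upper = 1.30 × baseline, lower = 0.80 × baseline):
- Systolic: 1.30 × 180 = 234; 0.80 × 75 = 60.
- Diastolic: 1.30 × 90 = 117; 0.80 × 40 = 32.

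**Step 2. Baselines from which an untriggered reading can lie outside the entry limits:**
- Systolic 181 or more: 181/1.30 = 139.2, so baselines 140-180.
- Systolic 74 or less: 74/0.80 = 92.5, so baselines 75-92.
- Diastolic 91 or more: 91/1.30 = 70.0, so baselines 70-90.
- Diastolic 39 or less: 39/0.80 = 48.75, so baselines 40-48.

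**Step 3. Examples that trigger nothing:**

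| Before | After | Systolic change | Diastolic change |
|---|---|---|---|
| 150/88 | 190/110 | 190/150 - 1 = +26.7% | 110/88 - 1 = +25.0% |
| 130/80 | 160/102 | 160/130 - 1 = +23.1% | 102/80 - 1 = +27.5% |
| 90/48 | 73/39 | 73/90 - 1 = -18.9% | 39/48 - 1 = -18.8% |

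The second row shows that an extreme baseline is not needed on the diastolic side.

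**Step 4. Release after a flag on a rise** (below 1.20 × baseline):
- Systolic: 1.20 × 180 = 216, so the highest release value is 215. Release above 180 needs 181 < 1.20 × baseline, that is baselines 151-180.
- Diastolic: 1.20 × 90 = 108, so the highest release value is 107. Release above 90 needs 91 < 1.20 × baseline, that is baselines 76-90.
- Example: 170/86 rising to 222/112 (+30.6%/+30.2%) is flagged. At 203/103 (+19.4%/+19.8%) monitoring may end.

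**Step 5. Other safeguards.** I looked for a post-immersion mmHg limit elsewhere and found none. The 10-minute check after leaving the water is of rectal temperature. The heart-rate rules, such as "If HR increases > 60 beats/min above resting", apply during heating. Staff monitor for adverse events throughout, and a CTCAE grade of 3 or more stops the procedure, but neither provision sets a pressure for discharge.

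**Step 6. How often the rule is used.** 20 participants × 8 sessions = 160, and 20 × 10 = 200 post-session readings. This counts applications of the rule, not occurrences of the gap.

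**The case against.** **The entry limits are not discharge limits.** They screen people before a 45-minute heat stress. Someone who arrives at 102 diastolic is only kept out of the water; the protocol orders no monitoring for that person. This stands. A reader might infer that the protocol contradicts itself by sending people home at a pressure that would bar entry. The text does not support that, because the two sets of rules serve different purposes. What remains is that no absolute exit limit of any kind exists.

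**The 10-minute sentence may cover everyone.** It does not say that it is confined to flagged participants. Read alone, it would send anyone still away from baseline at 10 minutes to a provider, including the 190/110 case. This stands as an ambiguity. The sequential reading is the more natural one: the sentence follows the percentage trigger, and a repeat reading is required only of those already flagged. Likewise, if return to baseline is taken literally, more flagged participants reach a provider than Step 4 suggests. On either reading the rule stays relative.

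**Participants are not unwatched.** ClearSight recording after sessions, the temperature follow-up, adverse-event monitoring and the emergency call all exist. A reader might infer that people leave with no monitoring at all, and that would be wrong. What is missing is a mandated blood-pressure recheck with an action limit. The emergency call covers overt impairment, which an asymptomatic 190/110 need not meet.

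**Possibility is not likelihood.** The high-side examples need rises of about 23% to 30%, and the low-side gap needs a low baseline. The protocol gives no distribution of post-immersion pressure, so a reader cannot infer that such discharges will be common.

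**A relative trigger is a legitimate choice.** Agreed, and the fix keeps it.

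**Conclusion.** The point holds as a weak safety rule, not as an error or a contradiction. Followed as written, and with the 10-minute sentence read in sequence, the rule allows discharge with no mandated recheck or provider discussion at readings such as 190/110 or 73/39. It allows release after a flag at up to 215 systolic or 107 diastolic. The affected baselines are 140-180 or 75-92 systolic and 70-90 or 40-48 diastolic. The high-side ranges are admissible at entry; the low-side gap is probably the rarer.

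The conclusion rests on two readings of unclear text: what baseline means, and whom the 10-minute sentence covers. The widest reading of that sentence would narrow the gap but leave staff with an ambiguous instruction and no number. No frequency is claimed, and there is no consequence for the VO2 result, the sample size or the analysis. I would put it to the sponsor as an optional, inexpensive improvement, with medium confidence.

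**What to change.** In Hot Water Immersion Therapy, keep the relative limits and the emergency-call rule unchanged, and make three additions:

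1. To the monitoring trigger, add: *or if any post-therapy reading is < 75 or > 180 mmHg systolic, or < 40 or > 90 mmHg diastolic*.
2. Before discharge, require return inside those limits or discussion with a medical provider.
3. State that the 10-minute provider discussion applies to everyone who meets either trigger.

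All three examples in Step 3 would then be flagged, and the 203/103 case could not leave without a provider discussion.

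**Cost.** A short amendment and a staff briefing. The post-therapy reading is already taken, so only newly flagged participants need repeat readings. The protocol says of immersion effects on the circulation that "These effects are normalized shortly after removal from the water and heat sources", so the added stay should usually be brief. The downside is at the diastolic ceiling: 90 to 91 is +1.1% and would now be flagged, so a few participants just above 90 will stay a little longer or need a brief provider discussion. If the sponsor finds 90 too tight for exit, it can state a different absolute diastolic limit.
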